**21.0 Informed Consent Process**

Once a potential participant is deemed eligible for participation, and agrees to participate, they will be informed that prior to participation an informed consent is required. A member of the research team will obtain the informed written consent and provide a copy of the consent document with the contact information for the PI and the University of Houston IRB. Although no measures for obtaining ongoing consent will be obtained, the consent form will be reviewed at the first visit of the intervention and again at posttest 1. This protocol will be following the SOP: Informed Consent Process for Research.

***Adults Unable to Consent***

As stated in the procedures, it may be necessary, per the NH requirements, to seek consent from durable powers of attorney. Although the recruitment of participants is for mentally alert residents, if they have given durable power of attorney to others, it may be necessary to obtain informed consent from their designated durable powers of attorney. Many residents execute a health care plan, including a durable power of attorney when they enter a NH and appoint a family member or someone to act on their behalf if they lack decision-making capacity. If necessary, a member of the research team will meet with the durable power of attorney to explain the research study and obtain written consent.

**22.0 Process to Document Consent in Writing**

This study will follow the SOP: Written Documentation of Consent (HRP-091). (*Please see the attached informed consent document*).

Supplemental consent form for media piece at presentation of results (*Please see attached supplemental consent form*).

**FULL PROTOCOL TITLE:** The Effectiveness of Life Story Book on Depression and Meaning in Life for Mentally Alert Residents of Nursing Homes

## **23.0 HIPAA**

N/A

## **24.0 FERPA**

N/A

## **25.0 Data Management**

Data will be analyzed using IBM SPSS Version 25 [49] and a multivariate analysis of covariance (MANCOVA) will be performed. Descriptive analysis will be conducted to describe participants, including demographic characteristics and their functional status (ADL). Demographic variables will be assessed with t-tests for independent samples (continuous variables) and chi-squared (categorical variables) to determine baseline differences. Prior to conducting the main analysis, data will be evaluated to ensure that assumptions for multivariate tests are fulfilled, including normality, linearity, univariate and multivariate outliers, homogeneity of variance-covariance matrices, and multicollinearity. Data will be inspected for any errors in data entry and for any missing data. Any reasons for withdrawal from the study and the loss to follow-up will be recorded.

A one-way MANCOVA will be performed to test for differences between the experimental group (LSB) and the control group on the 2 outcome measures (GDS-12R and MLQ), while using pre-test scores as covariates. Main effects from pre-test to post-test in both groups will be examined. To look at long term effects, repeated t-tests will be conducted at post-test 2.

Thematic analysis of the qualitative question will be conducted by the research team to identify themes in the data concerning the experience of participating in LSB.

Only the research team will have access to the encrypted and password protected database on which the study information will be stored. All members of the research team will be trained in appropriate data management techniques and the importance of maintaining confidentiality of data. All data will be inputted by the PI and then independently reviewed for accuracy by another member of the research team.

Eligibility screeners, consent documents, and documentation for receipt of the completed LSB will contain participants names (not ID numbers), and they will be kept separate from all other study information in a locked filing cabinet in the PI's office (345A SOCW) until after the study where they will be scanned and kept on an encrypted and password protected file on SharePoint, and maintained by my faculty advisor.

The code book with the name and the ID number of the participant will be kept in a separate locked filing cabinet in SOCW room 333, and will be destroyed following data collection.

Completed study instruments will only contain the participants' ID number and will be kept on an encrypted and password protected file on the UH SharePoint site. Any data or documentation relating to this study will not be accessed by anyone but the research team.

**FULL PROTOCOL TITLE:** The Effectiveness of Life Story Book on Depression and Meaning in Life for Mentally Alert Residents of Nursing Homes

Study transcripts will be de-identified with only the participant's ID number and will be maintained for a period of three years, per UH policy, following the conclusion of data collection, in an encrypted and password protected file on SharePoint, and maintained by my faculty advisor.

The PI will obtain a copy of the study data and documentation, with no identifiable information, on an encrypted CD

All data management procedures were more fully described in the previous section on 'Confidentiality'.

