## **5.0 Number of Subjects**

Two nursing homes will be recruited for comparison of LSB with care as usual. A power analyses for a MANOVA, with 2 groups and 2 dependent variables, was conducted in G\*Power Version 3.1.9.2 [32] to determine a sufficient sample size. Using an alpha ( $\alpha$ ) of .05, and a large effect size of  $d = .94$  [33], a sample size of 20 could achieve a power of 95% to detect between group differences.

Prior research in long-term care facilities indicates that oversampling by 15-20 percent is an efficient way to deal with attrition. This study will recruit 24 residents, or 12 residents per NH, to ensure a sample size of 20. From these two NHs, a minimum of 20 NH residents (10 per NH) and a maximum of 24 NH residents (12 per NH) will be recruited.

**FULL PROTOCOL TITLE:** The Effectiveness of Life Story Book on Depression and Meaning in Life for Mentally Alert Residents of Nursing Homes

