## **10.0 Procedures Involved**

### *Study Design:*

A quasi-experimental switching replication design will be employed to examine the effects of LSB on depressive symptoms and MIL for residents of NHs who are mentally alert by comparing post-test scores, while controlling for pretest scores. Two comparable NHs will be randomly allocated to NH-A or NH-B, indicating which home will begin LSB first, whereas the other home will receive care as usual. Participants in the same NH will receive the same intervention. A summary of the design is as follows:

Nursing Home A (NH-A):	Pretest	LSB	Post-test	CAU	Post-test
Nursing Home B (NH-B):	Pretest	CAU	Post-test	LSB	Post-test (CAU = care as usual)

Both NHs will eventually receive the LSB intervention, which will provide another opportunity to test outcome measures and allow for two independent implementations of the LSB intervention. This is one of the more ethically feasible designs because all participants will eventually receive the intervention. Furthermore, the additional post-test for NH-A, after one month, will examine the lasting effects of the LSB intervention.

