NH-B participants will be scheduled for post-tests in 4 weeks, which will include repeating an overview of the study, including the number of sessions and length of time for each session. A written postcard will be given to each participant with the date, time and contact information of their RA for their scheduled post-test. A follow-up postcard will be sent to the participant each week until week # 4, when a reminder phone call will also be made by their RA the day before their visit is scheduled. Until that time, the resident will continue to receive care as usual in their NH.

*Description of the Intervention:*

**Life Story Book.** LSB provides a person the opportunity to chronologically share their life experiences and memories [25]. The LSB will include a combination of written information, photographs of significant people, places or events, and personal narratives from the stages of life that the participant would like to include.

The duration of the intervention will be three-1-hour visits, not including the visits for the pretest and the post-tests measures collected, for a total of five visits. Each visit will begin with the RA assessing the environment and the participant's needs, making sure that the participant can hear and see the RA, and that the seating arrangement is comfortable before beginning. Assessing the environment will include: assessing for privacy, lighting, noise level, temperature and seating arrangement [39]. It will be important to monitor the participant's needs for any other difficulties assessed that may need to be tended to and adjustments or accommodations made. This is crucial to adequately accommodate the older adults' needs. Again, the RAs will remain flexible in regard to the length of time per visit for the sake of the older participants. For example, two 30-minute sessions may be used, as could rescheduling for health issues, or other creative ways to accommodate the needs of the participant as much as possible.

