**Geriatric Depression Scale (Residential) (GDS-12R)** is a shortened version of the 30item Geriatric Depression Scale which has been shown to effectively distinguish depressed from non-depressed older adults [43]. In 1986, a short form of 15-items (GDS-15) was developed for older adults, from the original 30-item questionnaire, primarily for brevity and for use with older adults with health issues or those with dementia. It was found to have a high correlation with depressive symptoms in previous validation studies [44]. Three items were found to not be reflective of residents of nursing homes and these three were omitted from the GDS-15 to create the GDS-12R, which increased the alpha from .76 to .81 [45]. The GDS-12R was found to have good internal consistency and test-retest reliability [45]. It is a self-report scale of depressive symptoms and uses a yes/no format. The scale measures how the person has felt during the previous week and usually takes 5 to 7 minutes to complete, making it ideal for older adults in residential facilities. Scores  $\geq 5$  are significant for depressive symptoms [46].

**Meaning in Life Questionnaire (MLQ)** will be used to measure MIL. Steger et al. MLQ [47] has two subscales which assess the presence of meaning (how much a person feels their life has meaning) and the search for meaning (how much a person strives to find meaning and understanding in their life) [48]. The two-subscale measure consists of 10 items on a 7-point Likert scale, ranging from 1-absolutely true to 7-absolutely untrue: five items for presence of meaning and five items for search for meaning. This questionnaire has been shown to have high convergent and discriminant validity and has been tested across age, gender, race, and national groups [47], [48]. The MLQ questionnaire does not have cut off scores like the Geriatric Depression Scale, but based on numerous studies, a score  $> 24$  indicates a person feels their life has meaning and purpose [48].

The GDS-12R and MLQ will be administered by the PI at three times; pre-test, post-test 1, and post-test 2. These measures will be administered orally to each participant and answers recorded by the PI on a tablet.

One open-ended feedback, qualitative, question will be asked of participants at post-test 2: "What did you think of the experience of participating in Life Story Book?" This question will be documented in writing with no names or ID numbers recorded.

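### With one nursing home per condition, the post-test 1 MANCOVA cannot separate Life Story Book from home; 1.0 and 25.0 set no limit on the conclusion, and 25.0 leaves the switch-phase analysis ambiguous

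*Combined protocol and SAP*

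**What the plan says.** - **Units.** Section 5.0: "Two nursing homes will be recruited for comparison of LSB with care as usual", with 10 to 12 residents per home. Section 10.0 (Study Design): "Two comparable NHs will be randomly allocated to NH-A or NH-B, indicating which home will begin LSB first". All residents of a home share one condition.
- **Design label.** Section 10.0: "A quasi-experimental switching replication design will be employed". The switch is justified because it will "allow for two independent implementations of the LSB intervention". Lasting effects are tied to one home: "the additional post-test for NH-A, after one month, will examine the lasting effects of the LSB intervention".
- **Timing.** Section 10.0: "NH-B participants will be scheduled for post-tests in 4 weeks".
- **Analysis.** Section 25.0: "A one-way MANCOVA will be performed to test for differences between the experimental group (LSB) and the control group", on GDS-12R and MLQ, with pre-test scores as covariates. The post-test is not named. Section 25.0 also plans to examine main effects between pre-test and post-test in both groups, and to run repeated t-tests at post-test 2 for long-term effects.
- **MLQ.** Section 10.0 describes two five-item subscales with responses "ranging from 1-absolutely true to 7-absolutely untrue", and says a score above 24 indicates meaning and purpose.
- **Objectives.** Section 1.0 aims to determine whether LSB has a greater and more lasting effect than care as usual. It has separate hypotheses for depression and for meaning in life.

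**The concern.** The MANCOVA judges the difference between two homes against variation among residents within homes. Anything that happens in one home between pre-test and post-test 1 (staffing, an outbreak, a change in activities) enters the group difference in full but not the error term. A significant result would be explained as well by such a change as by LSB, yet neither 1.0 nor 25.0 limits what may be concluded.

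The design's own partial answer is the switch, and here 25.0 is unclear. The pre-test to post-test analysis names no post-test. The post-test 2 t-tests are labelled long-term, although NH-B has only just had LSB by then. With three time points and two outcomes, the comparison could be chosen after the data are seen. For the MLQ, agreement in direction cannot even be defined until the scoring is settled.

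**Working it through.** **1. The plan's own figure.** Section 5.0 gives N = 20 for 95% power (MANOVA, 2 groups, 2 outcomes, alpha .05, effect size .94). For a noncentral F with df 2 and N − 3 and noncentrality N × f², entering .94 as f² gives power .952 at N = 20 and .939 at N = 19, so the figure reproduces. It treats residents as independent and has no home component. (Whether .94 was meant as d is a separate matter.)

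**2. Confounding, with no assumed value.** At post-test 1 the columns intercept, LSB and home have rank 2 of 3. Two homes for two conditions leave 2 − 2 = 0 between-home degrees of freedom, however many residents are recruited. All three time points give 2 × 3 = 6 cell means. Intercept, home, two time effects, current LSB and carry-over use all 6, so a home-by-time effect cannot be tested there either.

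**3. False rejections if homes change differently.** Assumptions: pre-post correlation r = .6, between-outcome correlation .5, two pre-test covariates, F on 2 and N − 5 df. A share s of residual variance is home-by-period variation. There is no LSB effect.

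| s | 0 | .01 | .02 | .05 | .10 |
|---|---|---|---|---|---|
| 10 per home | 5.0% | 6.1% | 7.3% | 11.7% | 19.1% |
| 12 per home | 5.0% | 6.3% | 8.1% | 13.6% | 23.1% |

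These are simulated, and independent runs agree within simulation error. The SD of the between-home difference is √[2 × s/(1 − s) × (1 − r²)]. At s = .05 this is √(2 × .0526 × .64) = .26 outcome SD.

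**4. False rejections from a stable home difference.** Covariate adjustment removes only a fraction r of a stable difference. A .5 SD difference on both outcomes leaves .5 × (1 − .6) = .20 SD. With no home-specific change at all, the simulated rejection rate is about 7 to 8%.

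**5. SE multipliers.** The variance of the home difference is (2σ²/n) × [1 + n × s/(1 − s)], so the SE is multiplied by √[1 + n × s/(1 − s)]. For s = .01/.02/.05/.10 this gives 1.05/1.10/1.24/1.45 (n = 10) and 1.06/1.12/1.28/1.53 (n = 12).

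**6. What the switch phase can add.** For NH-B, let (a) be the change from pre-test to post-test 1, (b) from post-test 1 to post-test 2, (c) = b − a, and (d) from pre-test to post-test 2. Let (e) be the NH-B minus NH-A change from post-test 1 to post-test 2. Variances in SD² units are 2(1 − r)/n for (a), (b) and (d), 6(1 − r)/n for (c), and 4(1 − r)/n for (e). At r = .6 the SEs with 10/12 residents are .28/.26, .49/.45 and .40/.37 SD.

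- (c) and (e) share post-test 1 with the MANCOVA. Each agrees in direction, per outcome, in about 82 to 84% of pure-chance rejections. With a true .94 SD effect, (c) agrees in about 99%, so the check discriminates poorly.
- Suppose a one-off .5 SD adverse event in NH-B at post-test 1 and no LSB effect. The MANCOVA then rejects in 22% (n = 10) or 27% (n = 12) of trials. (c) agrees in 98% of those and (d) in about 40%. If both homes also improve by .25 SD per phase, (d) agrees in 92 to 94%.

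**7. MLQ direction.** A five-item subscale runs from 5 × 1 = 5 to 5 × 7 = 35. With 1 as true and 7 as untrue, a higher score means less meaning. The cut-off above 24 makes a higher score mean more. Section 25.0 does not say which subscale, or whether a total, is analysed.

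**The case against.** **The design is openly quasi-experimental and takes precautions.** Section 29.0 requires homes comparable on five aspects, the order is randomised, both research assistants work in both homes, one person administers all measures, and pre-test scores are covariates. These reduce the problem. They do not remove it, because matching and covariates address baseline differences rather than events in one home during follow-up. The design label in 10.0 is not carried into 1.0 or 25.0.

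**The inflation is assumed.** This stands. The documents give no ICC, and at 1 to 2% the effect is small. A reader might infer that a false-positive rate near 20% has been shown; it follows only from a 10% share.

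**The text on the switch is ambiguous, not silent.** This also stands. Main effects in both groups could cover (a), and repeated t-tests could be paired tests covering (b) or (d). A reader might infer that 25.0 plans no analysis of NH-B's LSB phase; the wording does not support that.

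**NH-B's phase is not the only other information.** A reader might think so, but 10.0 shows NH-A in care as usual while NH-B receives LSB. Their concurrent changes can be compared. That removes drift common to both homes without needing equal phase lengths, but it includes any carry-over in NH-A. The attached timeline that the protocol cites is not in the public document and may settle the phase lengths.

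**A caveat does not alter the error rate.** Correct, and this limits how serious the point is.

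**Conclusion.** The point holds, as one that should be fixed. That LSB and home are one variable at post-test 1, with 0 between-home degrees of freedom, follows from 5.0 and 10.0 alone. The nominal 5% level needs two conditions: no home-specific change between pre-test and post-test 1, and full adjustment for stable home differences. No analysis of this contrast can restore it. The size is known only under assumption: from negligible to about 19% (10 per home) or 23% (12 per home) over shares of 0 to 10%, and about 7 to 8% from a stable .5 SD difference.

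Two stronger readings are tempting. One is that the MANCOVA should be dropped or the trial is uninterpretable. The documents describe a small quasi-experimental study whose planned comparison is usable if it is reported as a comparison of two homes. The other is that agreement in NH-B would establish effectiveness. It would not, because (c) and (e) share post-test 1 with the main test, and (d) is not corrected for drift. The remedy limits the inference and fixes choices in advance; it does not change the false-positive rate.

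**What to change.** 1. **Limit the conclusion (1.0 and 25.0).** State that the post-test 1 MANCOVA compares two nursing homes, that home effects cannot be separated from LSB, and that p-values treat residents as independent and are conditional on these two homes. State that a significant result will be reported as a difference between these two homes consistent with an LSB effect, not as proof of effectiveness. Name post-test 1 as the time point. Keep the MANCOVA as the planned test.
2. **Name the switch-phase estimates (25.0).** For each outcome, report (a) to (e) with mean and 95% CI and no decision rule. State their limits: (c) and (e) share post-test 1 with the MANCOVA; (e) removes common drift but includes carry-over in NH-A; (d) avoids post-test 1 but is not drift-corrected; all are imprecise with 10 to 12 residents. Restrict long-term effects at post-test 2 to NH-A, as 10.0 does.
3. **Settle the MLQ before data are seen.** Name the score to be analysed, and reconcile the response anchors with the cut-off.
4. **Optional.** Add the SE multipliers from step 5 as a sensitivity table, labelled as assumed values that do not cover under-adjustment for stable home differences.

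Cost: wording, some differences of scores already collected, and at most one small table. No new residents, visits or staff are needed, and the power of the MANCOVA is unchanged. The downside is a more limited conclusion and a little more analysis.

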**1.0 Objectives**

The purpose of this research is to test quantitatively the effectiveness of the Life Story Work (LSW) intervention, with a book product (LSB), for reducing depression and increasing meaning in life (MIL) for mentally alert nursing home (NH) residents.

The overall objective is to improve the quality of life for residents of NHs by determining whether the LSB intervention will have a greater and longer lasting effect compared with care as usual (i.e., decreased depression and increased meaning in life).

Hypothesis I LSB will lead to greater reductions in depressive symptoms than care as usual.

**FULL PROTOCOL TITLE:** The Effectiveness of Life Story Book on Depression and Meaning in Life for Mentally Alert Residents of Nursing Homes

Hypothesis II LSB will lead to a greater increase in MIL than care as usual.

My central hypothesis, formulated from my preliminary research, is that the LSB intervention will improve the quality of life for mentally alert NH residents and will have longer lasting effects than care as usual. If effective, it may offer a non-pharmacological intervention for improving care and quality of life for NH residents.

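### The aim of showing that LSB lasts longer than care as usual cannot be tested: no LSB-free group remains at post-test 2, and the repeated t-tests name no group or contrast

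*Combined protocol and SAP*

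**What the plan says.** Section 1.0 gives the overall objective as "determining whether the LSB intervention will have a greater and longer lasting effect compared with care as usual". The central hypothesis in the same section says that LSB "will have longer lasting effects than care as usual". Hypotheses I and II, also in 1.0, concern only greater change in depressive symptoms and in meaning in life; neither refers to duration.

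Section 10.0 (Study Design) sets out a switching replication with one home per sequence. NH-A has pretest, LSB, post-test, care as usual, post-test. NH-B has pretest, care as usual, post-test, LSB, post-test. It states that "Both NHs will eventually receive the LSB intervention" and that "the additional post-test for NH-A, after one month, will examine the lasting effects of the LSB intervention". The description of procedures in 10.0 adds that "NH-B participants will be scheduled for post-tests in 4 weeks", which is the care-as-usual period in that home. The outcome schedule is fixed: "The GDS-12R and MLQ will be administered by the PI at three times; pre-test, post-test 1, and post-test 2".

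Section 25.0 plans a one-way MANCOVA of LSB against control with pretest scores as covariates. On durability it says only: "To look at long term effects, repeated t-tests will be conducted at post-test 2".

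**The concern.** The objective is comparative: it asks whether the effect of LSB outlasts what care as usual would produce. That needs a group still on care as usual when durability is assessed, and the schedule has none at post-test 2. The analysis sentence does not say which home is tested, whether the tests are paired or between homes, or whether post-test 2 is set against pretest or post-test 1.

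Two things are at stake. A report written against 1.0 could claim longer lasting benefit than care as usual from data that cannot show it. And because the tests are undefined, the group and contrast could be chosen after the scores are seen, on two outcomes.

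**Working it through.** **Who is LSB-free at each assessment (design table in 10.0).**

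| Assessment | NH-A | NH-B | LSB versus care-as-usual contrast? |
|---|---|---|---|
| Pretest | before LSB | before LSB | baseline |
| Post-test 1 | after LSB | after care as usual | yes |
| Post-test 2 | about one month after LSB | after its own LSB | no |

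There is no fourth assessment. The only LSB versus care-as-usual contrast is therefore at post-test 1.

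**The possible readings of the t-tests.**

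1. Paired tests within NH-A. The change from pretest to post-test 2 has two segments. In the first, up to post-test 1, NH-B on care as usual is a concurrent comparison. In the second, post-test 1 to post-test 2, there is none. Persistence is a question about the second segment.

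2. NH-A against NH-B at post-test 2. Suppose LSB shifts the outcome by .94 SD in either home and NH-A keeps a share r of it. The expected difference in favour of NH-B is .94 × (1 − r):
   - r = 1: .94 × 0 = 0
   - r = .5: .94 × .5 = .47 SD
   - r = 0: .94 × 1 = .94 SD

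   A fully lasting effect gives no expected difference and a vanished effect gives the largest one. The test compares LSB a month ago with recent LSB. With 10 per home its two-sided power at .05 is .51 for r = 0 and .17 for r = .5.

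3. Paired tests within NH-B from post-test 1 to post-test 2. These repeat the immediate effect in the second home and carry no information on duration.

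**Precision of reading 1.** Inputs: n = 10 to 12 per home (5.0); correlation between assessments ρ = .5 to .7 (my assumption; the documents give none); equal SD at each assessment, set to 1.

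- SD of the paired difference = √(2(1 − ρ)): √1.0 = 1.000 at ρ = .5; √0.6 = .775 at ρ = .7.
- 95% confidence interval half-width = t(.975, n − 1) × SD / √n.

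| n | ρ = .5 | ρ = .7 |
|---|---|---|
| 10 | .715 | .554 |
| 12 | .635 | .492 |

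As an illustration, suppose half of a .94 SD effect (.47 SD) were lost between the post-tests. A two-sided paired t-test at .05 would detect the loss with power .265 to .403 at n = 10 and .318 to .483 at n = 12.

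**Status of the .94.** Section 5.0 gives no figure for durability; its sample size concerns the two-group MANOVA. With noncentral F, df 2 and 17, and noncentrality .94 × 20 = 18.8, power at N = 20 is .952, which reproduces the stated 95%. That requires .94 to be entered as f². As a standardised difference on one outcome, f² = .94²/4 = .221 and power at N = 20 is .388. So .94 SD is a scenario here, not a planned effect. The half-widths do not depend on it.

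**The case against.** The strongest defence is that the documents already narrow durability. Section 10.0 calls the design quasi-experimental, gives the ethical reason for treating both homes, and assigns lasting effects to NH-A's extra post-test after one month. The stated hypotheses make no durability claim. On this view the defect is loose wording in 1.0 and one undefined sentence in 25.0. That stands, and it limits how serious the point is. It does not remove it, because 1.0 still names care as usual as the comparator.

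Three stronger readings are tempting and should not be adopted.

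- A reader might infer that the t-tests are definitely paired tests in NH-A. This is the most natural reading: 10.0 ties lasting effects to NH-A, and 25.0 specifies independent samples where it means them ("Demographic variables will be assessed with t-tests for independent samples (continuous variables"). But that sentence concerns baseline demographics, and 25.0 names no group for post-test 2. The conclusion holds under every reading, so it need not rest on this one.
- A reader might infer that the whole pretest to post-test 2 change in NH-A is uncontrolled, and work out how often drift alone would look like benefit. NH-B is a concurrent comparison up to post-test 1, and the documents give no drift size. Such rates would be illustrative only, and I do not rely on any.
- A reader might infer that the main comparison fails too. It does not. Section 25.0 does not name the MANCOVA's post-test, but the design in 10.0 points to post-test 1, where NH-B is still on care as usual.

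**Conclusion.** The point holds as a mismatch between aim and design, and it should be fixed. The absence of an LSB-free group at post-test 2 follows directly from the schedule and needs no assumption. The plan can describe how NH-A scores move in the month after LSB; it cannot show that LSB lasts longer than care as usual.

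The precision statement (half-width .49 to .72 SD) rests on the assumed correlations of .5 to .7 and equal variances. It is enough to say that failing to find a decline would not establish persistence. Hypotheses I and II can still be addressed by the MANCOVA, taken to be at post-test 1.

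**What to change.** **Section 1.0.** Remove the claim of lasting longer than care as usual from the overall objective and the central hypothesis. Restate durability as a one-month follow-up of NH-A with no concurrent care-as-usual control after post-test 1.

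**Section 25.0.** Replace the repeated t-tests with two named NH-A contrasts for each outcome: post-test 2 minus post-test 1, and post-test 2 minus pretest. Report them as estimates with 95% confidence intervals. State that non-significance is not read as persistence, and that no between-home difference at post-test 2 is read as durability. Where NH-B's pretest to post-test 1 change is shown alongside, say that it is a concurrent comparison for the first segment only.

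Two additions are optional and not part of the fix: a note if the book is reviewed between NH-A's two post-tests, and an estimate of NH-B's change after its own LSB as a replication.

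**Cost.** Wording only, with no new data, visits or participants. The downside is a weaker durability claim.
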